2. A diagnosis or suspicion of immunodeficiency disorder either in the infant or in an immediate family member.
3. A diagnosis or suspicion of bleeding disorder that would contraindicate administration of bOPV or nOPV2 or collection of blood by venipuncture.
4. Acute diarrhoea, infection or illness at the time of enrolment (6 weeks of age) that would require infant's admission to a hospital.
5. Acute vomiting and intolerance to liquids within 24 hours before the enrolment visit (6 weeks of age).
6. Evidence of a chronic medical condition identified by a study medical officer during physical exam.
7. Receipt of any polio vaccine (OPV or IPV) before enrolment based upon documentation or parental recall.
8. Known allergy/sensitivity or reaction to polio vaccine, or its contents.
9. Infants from multiple births. Infants from multiple births will be excluded because the infant(s) who is/are not enrolled would likely receive OPV through routine immunization and transmit vaccine poliovirus to the enrolled infant. Even if all births from a multiple birth could be enrolled in the study, we will exclude multiple births as discontinuation of one may lead to discontinuation of multiple vaccine recipients.
10. Infants from premature births (<37 weeks of gestation).

Sibling

1. Participant in a previous poliovirus vaccine clinical trial.
2. Unable to participate in the study until and including the Clinic Visit at 10 weeks (age of vaccine recipient).
3. A diagnosis or suspicion of immunodeficiency disorder either in the sibling or in an immediate family member.
4. Acute diarrhoea, infection or illness at the time of enrolment that would require sibling's admission to a hospital.
5. Evidence of a chronic medical condition identified by a study medical officer during physical exam.

Discontinuation Criteria

Vaccine Recipient

1. Withdrawal of consent for participation for any reason.
2. Request by parents of vaccine recipient to terminate all study procedures.
3. Identification of immunodeficiency disorder, bleeding disorder or another medical condition for which continued participation, in the opinion of the principal investigator, would pose a risk to the vaccine recipient to continue in the study.
4. Receipt of immunosuppressive medications.

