Clinic Visit at 6 weeks of Age – Vaccine RecipientDate of visit (dd/MMM/yy): / / Date of birth (dd/MMM/yy): / / Sex: F / M**Demographics**

Father's education (circle): No formal school / Primary / Middle / High school / Graduate

Mother's education (circle): No formal school / Primary / Middle / High school / Graduate

Eligibility criteria for vaccine recipient

1. Child's residence within the study area? Yes / No
2. Child 6 weeks of age? Yes / No
3. Child and family NOT planning to travel / move in the next 3 months that would prevent them from coming for study follow-up visits? Yes / No
4. Child born in single birth? Yes / No
5. Child born after 37 weeks of pregnancy? Yes / No
6. No diagnosis or suspicion of immunodeficiency in the child or family member? Yes / No
7. Child has NO known coagulation disorders that contraindicates venipuncture or injection? Yes / No
8. Child has NOT received OPV or IPV before? Yes / No
9. Child does not have a medical condition that contraindicates bOPV or nOPV2 administration? Yes / No

If no, specify _____

10. Child has at least one sibling < 10 years living in the household? Yes / No

Is this child eligible for participation in the study as a vaccine recipient? Yes / No

- *Child is ELIGIBLE if all answers to questions 1-10 are YES. If the child is eligible, proceed to the next section.*
- *Child is NOT ELIGIBLE if any of the answers to questions 1-10 is NO. If the child is NOT eligible, STOP.*

Do the parents give consent for their child to participate in the study as a vaccine recipient? Yes / No

- *If parents DO NOT consent, ask them the following. When finished, thank them for their time and STOP.*

Why are you not interested in having your child participate in the study? (Circle all that apply) Study purpose unclear / Vaccine concerns / Reluctant to blood draw / More than two vaccine injections at first visit / Busy-No time / Other (specify): _____

- *If parents DO consent, continue with the study procedures.*

Clinic Visit at 6 weeks of Age – Vaccine Recipient

1. Is the child currently breastfed? No breastfeeding / Partial breastfeeding / Exclusive breastfeeding
2. Has the child received BCG? Yes / No
- 2a. If yes, date of vaccination (dd/MMM/yy): / /
3. Has the child received any other vaccine to date? Yes / No
- 3a. If yes, specify: _____
- 3b. Date of vaccination (dd/MMM/yy) / /
4. Has any other child in the household received OPV since the infant was born? Yes / No
- 4a. If yes, specify: _____

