- *Child is ELIGIBLE if all answers to questions 1-4 are YES. If the child is eligible, explain what the child's participation in the study will involve and provide the information sheet.*
- *Child is NOT ELIGIBLE if any of the answers to questions 1-4 is NO. If the child is NOT eligible, STOP. The sibling and vaccine recipient are not eligible to continue with study enrollment. Enrollment cannot continue for the vaccine recipient unless an eligible sibling is brought to the clinic to be enrolled on the same day.*

Do the parents give consent for their child to participate in the study? Yes / No

- *If parents DO NOT consent, ask them the following. When finished, thank them for their time and STOP.*

Why are you not interested in having your child participate in the study? (Circle all that apply) Study purpose unclear

Busy-No time / Other (specify): _____

- *If parents DO consent, continue with the study procedures.*

Polio vaccination history:

1. Is the vaccination card present? Yes / No

Note: If present, answer questions below based on the vaccination card.

2. Has the child ever received bOPV? Yes / No

2a. If yes, how many doses of bOPV? _____

2b. Date of most recent bOPV vaccination (dd/MMM/yy): / /

Clinic Visit at 6 weeks of Age – Sibling

3. Has the child ever received tOPV? Yes / No

3a. If yes, how many doses of tOPV? _____

3b. Date of most recent tOPV vaccination (dd/MMM/yy): / /

4. Has the child ever received fIPV? Yes / No

4a. If yes, how many doses of fIPV? _____

4b. Date of most recent fIPV vaccination (dd/MMM/yy): / /

5. Has the child ever received IPV? Yes / No

5a. If yes, how many doses of IPV? _____

5b. Date of most recent IPV vaccination (dd/MMM/yy): / /

Name and signature of medical officer: _____

Phone Call or Home Visit 24–48 hours after 6-week vaccination***To be completed for vaccine recipients in all Arms***Date of call/visit (dd/MMM/yy): / / Time of call/visit (hh:mm): **Adverse events**

Since the vaccine recipient was at the clinic for the “Clinic Visit at 6 weeks”, have they had any of the following symptoms?

1. Fever: No Yes If yes, please describe _____

If yes, and thermometer available: Grade 1: 37.5° C- 38.0 ° C Grade 2: 38.1° C- 39.0 ° C
 Grade 3: >39.0 ° C

2. Vomiting: No Yes If yes, Grade 1: 1 episode/24 hours Grade 2: 2-5 episodes/24 hours

Grade 3: ≥ 6 episodes/24 hours

3. Abnormal crying: No Yes If yes, Grade 1: < 1hour Grade 2: 1-3 hours

Grade 3: >3 hours

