2b. Date of vaccination (dd/mm/yy): / /
3. Has any other child in the household received OPV since the last clinic visit ? Yes / No 3a. If yes, specify: _____
4. Has the child had diarrhea in the last 24 hours (≥ 3 loose stools in 24 hours)? Yes / No
4a. If yes, specify: duration of diarrhea in days:
(If the child currently has fever $>38.3^{\circ}\text{C}$, blood in stools, vomiting or signs of dehydration, do not continue with study procedures. Provide advice and referral as required.)
5. Has the child been sick since the last study visit? Yes / No 5a. If yes, specify: _____
6. Is the child on any immunosuppressive medications? Yes / No 6a. If yes, specify _____

Physical Exam

7. Temperature: . $^{\circ}\text{Celsius}$
8. Length #1: . cm
9. Length #2: . cm
10. Weight #1: . kg
11. Weight #2: . kg

Blood Collection

12. Blood sample collected? Yes / No 12a. If not, why? _____
13. Sufficient quantity (1 ml)? Yes / No 13a. If insufficient, why? _____
14. Time of collection (hh:mm): :

Vaccine Administration*If Study Arm A or B*

15. nOPV2 administered? Yes / No 15a. If not, reason: _____
If administered: 15b. Time of vaccine administration (hh:mm): :
15c. Expiration (mmm/yy): /

If Study Arm B or C

16. bOPV administered? Yes / No 16a. If not, reason: _____
If administered: 16b. Time of vaccine administration (hh:mm): :
16c. Expiration (mmm/yy): /

Clinic Visit at 10 weeks of Age (ctd.)

17. Pentavalent administered? Yes / No 17a. If not, reason: _____

If administered: 17b. Dose: Penta1 / Penta2 / Penta3

17c. Site of administration: Right thigh / Left thigh

18. PCV administered? Yes / No 18a. If not, reason: _____

If administered: 18b. Dose: PCV1 / PCV2 / PCV3

18c. Site of administration: Right thigh / Left thigh

Observe for 30 minutes after vaccine administration:

19. Any symptoms? Yes / No

19a. If yes, specify (*complete Adverse Event Form, if required*): _____

The following questions correspond to sibling of the study vaccine recipient. Note: the sibling does not need to be present for this visit.

20. Has the child received any poliovirus vaccines (bOPV, fIPV) since last visit? Yes / No

20a. If yes, specify: / /

20b. Date of vaccination (dd/mm/yy): _____

21. Has the child had diarrhea in the last 24 hours (≥ 3 loose stools in 24 hours)? Yes / No21a. If yes, specify: duration of diarrhea in days

22. Has the child been sick since the last study visit? Yes / No 22a. If yes, specify: _____

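### The pass rules on the 6-week forms have no specific item for five of the protocol's own exclusions, so an excluded infant or sibling could pass; forms and criteria must be reconciled

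*Protocol*

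**What the plan says.** **Where eligibility is decided.** The Data Safety Monitoring Plan (Records to be kept) places the eligibility assessment at the beginning of the 6-week clinic form.

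**What excludes a child.** The Exclusion Criteria open with a pair rule: an exclusion in either child bars both. The infant's list has ten entries. Number 4 is "Acute diarrhoea, infection or illness at the time of enrolment (6 weeks of age) that would require infant's admission to a hospital", number 5 is "Acute vomiting and intolerance to liquids within 24 hours before the enrolment visit (6 weeks of age", and number 6 is "Evidence of a chronic medical condition identified by a study medical officer during physical exam". The sibling's list has five. Its medical entries are immunodeficiency (3), illness that would need admission (4), and a chronic condition found on examination (5).

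**What the forms require (Appendix A).** The infant form states "Child is ELIGIBLE if all answers to questions 1-10 are YES. If the child is eligible, proceed to the next section". The sibling form states "Child is ELIGIBLE if all answers to questions 1-4 are YES".

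**What follows the pass rule.** After the pass rule and consent, the infant form records diarrhoea (item 5), immunosuppressive medication (item 6) and temperature, length and weight (items 7 to 11). Allocation is item 15. None of items 5 to 11 carries a stop instruction. The 10-, 14- and 18-week forms do carry one, covering fever, blood in the stools, vomiting and dehydration.

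**Related text.** Discontinuation criterion 4 for the infant is "Receipt of immunosuppressive medications"; the entry list has no counterpart. In the enrolment visit under Study Procedures, the medical officer confirms eligibility at step 1, the arm is assigned at step 2, the first dose is given at step 6, and the sibling's clinical information and examination come at step 9.

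**The concern.** A form that says a child is eligible when a fixed set of answers is YES is a decision rule, and staff will apply it as printed. If that set is narrower than the protocol's criteria, the trial has two definitions of its population.

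The first dose is the only study exposure behind the one-dose immunogenicity comparisons (secondary objectives 1a and 2a) and behind the shedding, transmission and recombinant objectives (secondary 3 to 5). An oral dose given to an infant who is vomiting may be lost, which would lower measured response and shedding. Vomiting is also a solicited adverse event at 24 to 48 hours. With no record of it at baseline, vomiting already present cannot be told from vomiting that began after the dose.

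For siblings the stake is different. They receive no study vaccine, but their stool provides the transmission estimate, and under the pair rule an ineligible sibling makes the infant ineligible too.

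**Working it through.** The point disputes no figure in the plan. The check sets the exclusion lists beside the 6-week forms, item by item.

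**Infant: ten exclusions against form questions 1 to 10**

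| Exclusion | Form item |
|---|---|
| 1 cannot complete follow-up | question 3 |
| 2 immunodeficiency, self or family | question 6 |
| 3 bleeding disorder | question 7 |
| 4 acute illness needing admission | none |
| 5 vomiting and intolerance to liquids | none |
| 6 chronic condition on examination | none |
| 7 earlier polio vaccine | question 8 |
| 8 "Known allergy/sensitivity or reaction to polio vaccine, or its contents" | only through the general question 9 |
| 9 multiple birth | question 4 |
| 10 premature birth | question 5 |

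Count: 6 direct + 1 through question 9 + 3 with no specific item = 10. Question 9 asks whether a medical condition contraindicates either study vaccine. That may catch some of the children meant by exclusions 4 to 6, but it is a narrower test.

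**Sibling: five exclusions against sibling questions 1 to 4**

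| Exclusion | Form item |
|---|---|
| 1 earlier polio vaccine trial | question 4 |
| 2 cannot stay to the 10-week visit | question 3 |
| 3 immunodeficiency | not on the sibling form; reached by question 6 on the infant form, which asks about family members |
| 4 acute illness needing admission | none |
| 5 chronic condition on examination | none |

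Count: 2 direct + 1 through the infant form + 2 with no item = 5. Across both children, 3 + 2 = 5 exclusions have no specific item.

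**Does anything else at entry fill the gap?** The Screening Form has no medical question for either child. The 6-week infant form records diarrhoea and temperature, but after the pass decision and without a stop; vomiting appears nowhere on it. The 6-week sibling form has no examination section, so the sibling's examination has no place to be recorded there.

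**Order of events.** Sibling exclusion 5 depends on an examination. As listed, that examination (step 9) follows arm assignment (step 2) and the infant's first dose (step 6).

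**Would the analysis sets remove such a child?** The Primary Analytical Approach restricts on consent and adequate specimens. The Secondary Analytical Approach adds restrictions on specimen timing and on study vaccination. Neither contains an eligibility condition.

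**Effect on stated figures.** The 238 per group and the enrolment target of 265 (238 / 0.9 = 264.4, rounded up) rest on assumed response, margin, power and attrition. None of these depends on the forms.

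**The case against.** The protocol body is clear. The criteria must be met by both children, the medical officer confirms eligibility at step 1, and the sibling is examined at the visit. A conscientious officer would work from the protocol. This stands, and it limits the conclusion to what could happen. It does not remove the conflict, because the document names the form as the place of assessment and the form's rule is complete in itself.

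Stronger readings are tempting but not supported:

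- A reader might infer that excluded children will be enrolled. The officer's confirmation and question 9 stand in the way.
- A reader might infer that every medical exclusion for siblings is missed. That is true of the sibling form alone; question 6 on the infant form reaches immunodeficiency.
- A reader might infer that the first dose is the only one given unchecked. Exclusions 4 and 5 in the body apply at that visit; what is missing is a matching item or stop on the form. For later doses it is the body that has no rule matching the forms' stop note.
- A reader might infer that an infant on immunosuppressive medication must be randomised and then discontinued. On the form the medication item and the examination precede allocation, and the Randomization section reveals the arm only after enrolment procedures. The visit steps list assignment earlier, so the order is unclear rather than wrong.
- A reader might put a number on the infants affected. The documents give no rate, and a rate for any vomiting or illness on the day would be broader than exclusions 4 and 5, which require intolerance to liquids and need for admission respectively.

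**Conclusion.** The point holds as a contradiction between the protocol's entry criteria and the forms that apply them: 3 of 10 infant exclusions and 2 of 5 sibling exclusions have no specific item in the pass rules. A child the protocol excludes could pass, receive the first dose (if the infant) or contribute stool (if the sibling), and remain in both analysis sets as the protocol defines them. The Protocol Deviation Tracking Form has a category for eligibility errors, but it helps only if the error is noticed, and nothing on the 6-week form would show missed vomiting.

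The size of the effect cannot be computed from the documents. It is probably small. The same form is used before allocation in all arms, so any such children should be spread across arms by chance. No power, margin or endpoint figure is shown to change. The case for correction rests on consistency, safety screening and data quality. It assumes that the forms are used as printed. A statistical analysis plan, not seen here, might add an eligibility condition to the per-protocol set, but that would not repair the screen at entry.

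**What to change.** Reconcile the Exclusion Criteria with the 6-week infant and sibling forms so that each pass rule runs over every listed criterion. Put the examination of both children before the eligibility decision and randomisation, in the visit steps as well as on the forms, and give the sibling's examination a place to be recorded.

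Two neighbouring passages also need to agree: the entry list with discontinuation criterion 4 on immunosuppressive medication, and the stop note on the later forms with the 6-week form and the protocol body. Which clinical rule should apply in each case is for the investigators and the sponsor.

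The cost is a few added items on paper and in REDCap, some reordering, and a short amendment. Sample size and the analysis are unchanged. Some children may be screened out before randomisation.

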5. Receipt of any polio (OPV or IPV) vaccine outside of study after enrolment (as per parent's report). Vaccine recipients who received polio vaccines outside of the study, including any polio vaccine administered in polio campaigns, would be excluded from further study procedures.
6. Temporary discontinuation may occur when there has been a temporary suspension of study activities. Study enrolment will be suspended from 12 weeks before the start of polio campaigns in the study areas to 6 weeks after the completion of polio campaigns in the study areas. This measure is to prevent potential interference from polio vaccine administered during polio campaigns in the study areas. If vaccine recipients receive vaccine during polio campaigns, they would be discontinued from further study procedures.

7. Unable to collect or obtain blood at enrolment (Clinic Visit at 6 Weeks of Age).
8. Allergic reaction to a prior dose of polio vaccine, or its contents.
9. Premature termination of the study.

Sibling

1. Vaccine recipient is discontinued from the study.
2. Withdrawal of consent for participation for any reason.
3. Receipt of any polio (OPV or IPV) vaccine after enrolment (as per parent's report). Siblings who receive polio vaccines during their participation in the study, including any polio vaccine administered in polio campaigns, would be excluded from further study procedures.

Description of Study Vaccines

Two polio vaccines will be used in the study: bOPV and nOPV2

1. Bivalent oral polio vaccine (bOPV)

- a. Manufacturer: Bio Farma
- b. Presentation: the vaccine will be available in multi-dose vials
- c. Formulation: Each dose (2 drops = 0.1 ml).
- d. Administration: one vaccine vial will be used per participant.
- e. Previous use at icddr,b: bOPV is part of the routine immunization schedule in Bangladesh.

2. Candidate 1 novel monovalent oral poliovirus vaccine type 2 (nOPV2)

- a. Manufacturer: Bio Farma

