5. The vaccine recipient will receive the recommended routine childhood vaccinations, except polio vaccination. Routine polio vaccines will be replaced by the study vaccine.
6. Schedule the next visit.

Study Clinic Visit – 14 weeks of age [All arms]

During this visit, the following procedures will be conducted:

1. The medical officer will complete the eCRF and examine the vaccine recipient.
2. One blood specimen (1 ml) will be collected by venipuncture.
3. Study vaccines will be administered, as directed by study arm.
4. The vaccine recipient will be observed for 30 minutes to monitor for any adverse reactions to the study vaccine.
5. The vaccine recipient will receive the recommended routine childhood vaccinations, except polio vaccination. Routine polio vaccines will be replaced by the study vaccine.
6. Schedule the next visit.

Study Clinic Visit – 18 weeks of age [All arms]

During this visit, the following procedures will be conducted:

1. The medical officer will complete the eCRF and examine the vaccine recipient.
2. One blood specimen (1 ml) will be collected by venipuncture.
3. Completion of study activities.
4. Vaccine recipients in Arms A and B will be given the first of three bOPV doses. Note: Arm B will be given three doses of bOPV to account for possible immunologic interference during co-administration of bOPV with nOPV2. All vaccine recipients will be given the first of two fIPV doses.

Timing of Evaluations

Entry/eligibility evaluations

- Entry evaluations will be completed at 6 weeks of age.
- Blood collection and study vaccine administration are planned during the study entry evaluation at 6 weeks of age. Blood will be collected before administration of any study vaccines. On the date of enrolment, study vaccines will be administered only if adequate blood specimen has been collected. If blood cannot be collected on the day of enrolment, study vaccine recipients will be discontinued from the study.
- The window for entry evaluation including collection of blood and administration of vaccine is 42–48 days of age.

Post-entry evaluations and follow-up

- After the first enrolment visit (6 weeks of age, range 42–48 days), the window for study visits is +/- 3 days.
- Blood will be collected before any study or EPI vaccines are administered.
- Stool collection from vaccine recipients and one sibling each will take place at 8 and 10 weeks of age for all Arms, and additionally at 7 weeks for Arm A only.

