This is an open-label, non-inferiority, randomized clinical trial that will compare immune response to types 1, 2 and 3 polioviruses of nOPV2 and bOPV when co-administered compared to nOPV2 and bOPV given alone. The study will recruit 795 vaccine recipients in three arms. Vaccine recipients will be enrolled at 6 weeks of age and followed until 18 weeks of age, for 12 weeks of follow-up. For each vaccine recipient enrolled, one sibling will be enrolled at the same time and followed for 4 weeks .

General Analytical Issues

The data will be analysed by study investigators that include epidemiologists and statisticians. Statistical packages that will be used for the analysis include R, SAS and STATA.

For assessing immunity to polio, seropositivity is defined as reciprocal polio neutralizing antibody titers

of at least 1:8. Immune response will be defined as either seronegative vaccine recipients ($<1:8$ titers) who become seropositive ($\geq 1:8$) [seroconversion] or vaccine recipients who demonstrate a four-fold

increase in titer (boosting). Baseline maternal antibody titers will be determined at 6 weeks of age and the estimated maternal antibody level at each blood collection will be calculated assuming an exponential decline with a half-life of 28 days.

For assessing fecal viral shedding, detection of nOPV2 or bOPV vaccine virus in stool specimens from vaccine recipient or sibling at either 1, 2, or 4 weeks post-vaccination of the vaccine recipient at 6 weeks of age will be defined as positive for viral shedding. For assessing the detection of household transmission, presence of transmission will be defined as the sibling of the vaccine recipient testing positive for nOPV2 vaccine virus at either 1, 2, or 4 weeks post-vaccination of the vaccine recipient at 6 weeks of age.

To characterize the intertypic recombinants in a subset of stool specimens of vaccine recipients and siblings after one dose of nOPV2 given with or without bOPV, amplicon sequences from long-read sequencing methods will be used to confirm genome structure. Amplicon sequences will also be mapped against all three Sabin vaccine reference sequences to generate coverage plots.

Primary Analytical Approach

The primary analytical approach will be intention-to-treat. To evaluate the primary objectives, the intention-to-treat analysis will be restricted to vaccine recipients who:

- Have not withdrawn consent for receipt of vaccines and follow-up evaluations since enrolment.

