- Have adequate blood specimen for serological analysis from the enrolment visit at 6 weeks of age.
- Have adequate blood specimen for serological analysis from the follow-up visit as mentioned by arm by primary objective in Table 5.

For secondary objectives 1 and 2, the intention-to-treat analysis will be restricted to vaccine recipients who:

- Have not withdrawn consent for receipt of vaccines and follow-up evaluations since enrolment.
- Have adequate blood specimen for serological analysis from the enrolment visit.
- Have adequate blood specimen for serological analysis from the follow-up visit as mentioned by arm by secondary objective in Table 5.

For secondary objectives 3-5, the intention-to-treat analysis will be restricted to vaccine recipients and siblings who:

- Have not withdrawn consent for receipt of vaccines and follow-up evaluations since enrolment.
- Have adequate stool specimens to examine vaccine-virus particles.

Secondary Analytical Approach

In addition to an intention-to-treat analysis, we will also perform per protocol analysis. To evaluate the primary objectives, per protocol analysis will be limited to vaccine recipients with the same restrictions as that outlined in primary analytical approach for primary objectives with additional restrictions of:

- Adequate blood specimen for serological analysis within 3 days of the scheduled visit date. This applies to enrolment visit blood specimen as well as follow-up visit blood collection.
- Received all scheduled study vaccines within 3 days of scheduled visit date.

For secondary objectives 1 and 2, the per protocol analysis will be limited to vaccine recipients with the same restrictions as those outlined in the primary analytical approach for secondary objectives 1 and 2 with additional restrictions of:

- Adequate blood specimen for serological analysis within 3 days of the scheduled visit date. This applies to enrolment visit blood specimen as well as follow-up visit blood collection.
- Received all scheduled study vaccines within 3 days of scheduled visit date.

For secondary objectives 3-5, the per protocol analysis will be limited to vaccine recipients or siblings with the same restrictions as those outlined in the primary analytical approach for secondary objectives 3-5 with additional restrictions of:

- Adequate stool specimen to examine vaccine-virus particles within 3 days of the scheduled visit date.

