- Vaccine recipient received the scheduled study vaccination at 6 weeks of age.

Table 5: Study arms comparison, study endpoints, and results by objective

Study Objective	Study Arms Comparison	Endpoint (vaccine recipient age)	Results Included in Analysis
Primary			
1. To compare type 2 immunogenicity of two doses of nOPV2 with two doses of nOPV2 co-administered with bOPV.	A vs. B	14 weeks	Serology: 6, 10, 14 weeks
2. To compare type 1 and 3 immunogenicity of two doses of bOPV with two doses of bOPV co-administered with nOPV2.	C vs. B	14 weeks	Serology: 6, 10, 14 weeks
Secondary			
1. To compare type 2 immunogenicity of one or three doses of nOPV2 with the same number of doses of nOPV2 co-administered with bOPV.	A vs. B	10 weeks	Serology: 6, 10 weeks
		18 weeks	Serology: 6, 10, 14, 18 weeks
2. To compare type 1 and 3 immunogenicity of one or three doses of bOPV with the same number of doses of bOPV co-administered with nOPV2.	C vs. B	10 weeks	Serology: 6, 10 weeks
		18 weeks	Serology: 6, 10, 14, 18 weeks
3. To assess the presence of fecal viral shedding (as determined by real-time RT-PCR) over time following one dose of nOPV2, bOPV, or co-administered nOPV2 and bOPV.	Descriptive with comparisons of A vs. B and B vs. C	10 weeks (i.e. 4 weeks post-vaccination)	Stool: 7 (Arm A only), 8, 10 weeks from vaccine recipient
4. To estimate household transmission of nOPV2 by assessing the presence of fecal viral shedding (as determined by real-time RT-PCR) among siblings of vaccine recipients.	Descriptive	10 weeks (i.e. 4 weeks post-vaccination)	Stool: 7 (Arm A only), 8, 10 weeks from sibling
5. To assess the occurrence and genomic characteristics of intertypic recombinants in stool specimens of vaccine recipients and siblings after one dose of nOPV2 given with or without bOPV.	Descriptive with comparison of A vs. B	10 weeks (i.e. 4 weeks post-vaccination)	Stool: 8, 10 weeks from vaccine recipient and sibling

Adverse Events (AEs)

Safety will be assessed by:

- Incidence rate of solicited systemic AEs 24–48 hours after the first study vaccination.
- Incidence rate of unsolicited AEs during entire study period.
- Incidence rate of serious AEs during entire study period.

Data Safety Monitoring Plan (DSMP)

Records to be kept

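### The per-protocol set for the stool objectives keeps samples passed after a non-study polio vaccine dose, a discontinuation event that no form asks about until the 10-week clinic visit

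*Protocol*

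**What the plan says.** Discontinuation Criteria, vaccine recipient, item 5 covers "Receipt of any polio (OPV or IPV) vaccine outside of study after enrolment". Item 3 for siblings covers "Siblings who receive polio vaccines during their participation in the study", campaign doses included. Both rely on what the parent reports, and both act forward only: the child has no further study procedures.

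On timing, Timing of Evaluations states "Stool collection from vaccine recipients and one sibling each will take place at 8 and 10 weeks of age for all Arms", with an extra 7-week collection in Arm A, and after enrolment "the window for study visits is +/- 3 days". In Appendix A the first post-enrolment vaccine question for the infant is item 2 of the form for the 10-week clinic visit, with the date in 2b. For the sibling it is item 20 of the same form, "Has the child received any poliovirus vaccines (bOPV, fIPV) since last visit", with the date in 20b.

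In Data Analysis, the intention-to-treat set for secondary objectives 3 to 5 requires that consent has not been withdrawn and that participants "Have adequate stool specimens to examine vaccine-virus particles". The per-protocol set adds two conditions: the stool falls within 3 days of the scheduled visit, and "Vaccine recipient received the scheduled study vaccination at 6 weeks of age". Shedding is defined as "detection of nOPV2 or bOPV vaccine virus in stool specimens from vaccine recipient or sibling" at any of the post-vaccination time points.

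**The concern.** The protocol treats an outside polio dose as serious enough to end participation, yet the per-protocol set for the stool objectives does not remove samples passed after one. Because the question is first put at the 10-week clinic visit, the discontinuation rule cannot be relied on to stop those samples being taken.

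Two secondary results are exposed. For objective 3, virus from an outside bOPV dose counts as type 1 or 3 shedding following one study dose. For objective 5, Table 5 sets an A versus B comparison of intertypic recombinants in recipients and siblings. Arm A is the arm without study bOPV. The background section says that recombination needs one cell infected by two strains, so an outside bOPV dose in an Arm A child infected with nOPV2 supplies the second strain. A recombinant that followed would be counted in the nOPV2-alone arm and would narrow the contrast.

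**Working it through.** The plan has no figure to reproduce on this point. The check is a trace of forms and sets, followed by an illustration of size.

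**1. When the question is asked** (Study Procedures and Appendix A)

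| Contact | Content | Outside polio vaccine asked? |
|---|---|---|
| 24–48 h call or visit | symptoms and adverse events | no |
| 7-week household form (Arm A) | kit delivery, collection, date, time, quantity | no |
| 8-week household form | same | no |
| 10-week household form | same | no |
| 10-week clinic form | items 2/2b (infant), 20/20b (sibling) | yes, first time |

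The 7- and 8-week stools always precede the question. The 10-week home visit is listed before the 10-week clinic visit, but both fall at the same age with the same window, so the order at 10 weeks is not fixed by rule. Sibling participation runs to that clinic visit and no further, so an event first reported there leaves little for the sibling rule to prevent.

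**2. What the sets remove**

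- Intention-to-treat, objectives 3 to 5: consent not withdrawn, adequate stool.
- Per protocol: the above, plus stool timing and the infant's 6-week study dose.
- Neither names outside polio vaccine. The discontinuation tracking forms require a protocol deviation form for this event, but the per-protocol definition does not refer to deviations.

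**3. Whether the laboratory could separate the sources**

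Appendix C describes a Sabin multiplex real-time RT-PCR and mapping of reads to the three Sabin references. Nothing described distinguishes study bOPV from bOPV given elsewhere. In Arm A a type 1 or 3 signal is plainly not study vaccine given to that child, but the shedding definition still counts it.

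**4. Illustrative size**

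Enrolment per arm is 265 (Table 4). The protocol gives neither the proportion *c* of children dosed outside the study before the stool nor the proportion *s* of those who shed, so both are assumed. Affected children = 265 × *c* × *s*.

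| *c* | children dosed | affected, *s* = 30% to 80% | share of arm |
|---|---|---|---|
| 0.5% | 1.3 | 0.4 to 1.1 | 0.15% to 0.40% |
| 1% | 2.6 | 0.8 to 2.1 | 0.30% to 0.80% |
| 2% | 5.3 | 1.6 to 4.2 | 0.60% to 1.60% |
| 5% | 13.2 | 4.0 to 10.6 | 1.50% to 4.00% |

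For Arm A infants these are added type 1/3 positives. For infants in Arms B and C they are upper limits, because some of these children would be positive from the study dose anyway.

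For recombinants, suppose 50 Arm A children are sequenced (assumed; the protocol says only a subset). At *c* = 1% to 3%, 50 × 0.01 = 0.5 to 50 × 0.03 = 1.5 of them would have had an outside dose. One recombinant arising this way would be 1/50 = 2%, but an outside dose is several steps short of a detected recombinant.

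**The case against.** The strongest reply is that the exposure routes are mostly closed. Routine bOPV in Bangladesh is due at 6, 10 and 14 weeks, so no routine infant dose falls due between the 6- and 10-week visits, and the 10-week dose is replaced by study vaccine. Multiple births are excluded, so a sibling by the same mother is past the 14-week dose. Enrolment stops 12 weeks before a campaign and stools end 4 weeks after enrolment, so the last child enrolled finishes stool collection 12 − 4 = 8 weeks before the campaign starts. That leaves catch-up and off-schedule doses and unforeseen campaigns. This stands, and it is why the number is probably small.

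A parent may also volunteer the information at a home visit, and the sibling discontinuation form allows 7 or 8 weeks as the last visit. A reader might infer that the discontinuation rule does nothing for siblings. The documents show only that no form prompts for the event earlier.

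It can be said that the dates are recorded and the SAP, which is not available here, could use them. That would settle the matter if the protocol were silent. It is not: it lists the per-protocol conditions for objectives 3 to 5, and they keep these stools.

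Finally, a reader might infer that affected stools should leave both analysis sets. The protocol does not support that as a plain correction. Removing samples from an intention-to-treat set on a post-randomisation event, in an open-label trial where Arm A parents know their infant gets no bOPV, could itself unbalance the arms. The objection holds for that set but not for the per-protocol set.

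**Conclusion.** The point holds in a limited form. The protocol fixes a per-protocol set for secondary objectives 3 to 5 that retains stools passed after an event it treats as grounds for discontinuation, and its forms first ask about that event when the 7- and 8-week stools are already in hand. Non-study bOPV virus can therefore enter the type 1/3 shedding results in any arm and the A versus B recombinant comparison through Arm A.

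The protocol does not show that such virus does enter. Under the assumptions above, the effect ranges from under one child to about ten per arm (0.15% to 4.0%), and the schedule and the campaign pause favour the low end. Nor does one exposed child equal one recombinant: the child must also be co-infected, form a detectable recombinant and fall in the sequenced subset. The background section reports no recombination in the Panama sequencing, so Arm A counts may be low enough for one or two such children to show.

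The household transmission endpoint is defined on nOPV2 virus and is not affected by outside bOPV. The primary serology comparisons are outside this point. The results at risk are secondary and largely descriptive.

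**What to change.** 1. In the per-protocol definition for secondary objectives 3 and 5, exclude any recipient or sibling stool collected after the reported date of a non-study OPV dose, using items 2b and 20b of the 10-week clinic form.
2. Leave the intention-to-treat set as it is, and report its objective 3 and 5 results with and without the affected stools as a sensitivity analysis.
3. Keep the affected sibling stools for the type 2 transmission endpoint of objective 4.
4. Optionally, add the same one-line vaccine question for both children to the existing 7-, 8- and 10-week household forms, so that the discontinuation rule as written can act earlier.

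The cost is one sentence in the analysis-set definition, one extra table and, if wanted, one question on three existing forms. There is no new visit or sample. The downside is the loss of a few stools from two secondary per-protocol analyses.
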